Pharmacokinetic data: Irinotecan is converted into its active metabolite SN-38 in the liver by carboxylesterase enzymes [48]. SN-38 is subsequently converted to SN-38 glucuronide by uridine diphosphate glucuronosyltranferases (UDG). Although the majority of irinotecan is metabolized into SN-38 under normal circumstances, a small minority is converted into two minor metabolites by cytochrome P450 isoenzyme CYP3A4. Predictably, inducers of the CYP3A4 isoenzyme have been shown to lead to increased clearance of irinotecan and reduced levels of SN-38 [49, 50]. Use of CYP3A4 inducers should be avoided due to concerns for decreased efficacy of irinotecan.

Toxicity data: The dose limiting toxicities of irinotecan administered intravenously on adult schedules of once every 1-3 weeks are myelosuppression and diarrhea. When irinotecan is administered on a protracted schedule as done in pediatrics, myelosuppression is substantially

reduced while diarrhea remains the dose-limiting toxicity [51-53]. The addition of cephalosporin prophylaxis to various treatment regimens of irinotecan has increased the tolerability of protracted irinotecan by significantly decreasing the incidence of diarrhea, allowing for the escalation of the maximum tolerated dose (MTD) [44, 45, 54]. The active metabolite SN-38 is thought to act locally in the gastrointestinal tract, directly injuring the intestinal mucosa and leading to a secretory diarrhea [55]. Cephalosporins ameliorate irinotecan-associate diarrhea by limiting conversion of the inactive glucuronidated SN-38 to active SN-38 by glucuronidase producing enteric bacteria. Pediatric regimens using cephalosporins have shown significant reduction in severe diarrhea when antibiotics are started a few days prior to irinotecan, and continued for three days past the fifth chemotherapy day. [44, 45, 54]

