3. PATIENT SELECTION

3.1 Eligibility Criteria

- 3.1.1 Patients must \geq 13 and \leq 30 years of age at the time of study entry.
- 3.1.2 Patients must have a histologically confirmed solid tumor malignancy at either original diagnosis or relapse for which no curative therapy exists, and which has either recurred or progressed after at least one prior systemic therapy. Patients with primary brain tumors, or those with brain metastases at time of potential enrollment, are excluded. Additionally, patients with GIST, alveolar soft part sarcoma, or dematofibrosarcoma protuberans are excluded.
- 3.1.3 Patients must have either measurable or evaluable disease, as defined in Section 11.1.2.
- 3.1.4 Performance Level: ECOG performance status ≤ 2 (Karnofsky ≥60%, see Appendix A). Note: Patients who are unable to walk because of paralysis, but who are up in a wheelchair, will be considered ambulatory for the purposes of assessing the performance score.
- 3.1.5 Prior Therapy: No limit is placed on the number of prior therapies. Prior treatment with irinotecan or eribulin is allowed, although patients must not have received co-administration of eribulin and irinotecan and must not have had disease progression while receiving either eribulin or irinotecan.

Patients must have fully recovered from the acute toxic effects of all prior chemotherapy, immunotherapy, or radiotherapy prior to entering this study.

- a. Myelosuppressive chemotherapy: Must not have received within three weeks of start date of this protocol chemotherapy; six weeks is required after administration of nitrosourea agents.
- b. Hematopoietic growth factors: At least 7 days since the completion of therapy with a growth factor or at least 14 days for a long-acting growth factor (e.g. pegfilgrastim)
- c. Biologic (anti-neoplastic agent): At least 7 days or 3 half-lives since the completion of therapy with a biologic agent, whichever is longer. For agents that have known adverse events occurring beyond 7 days after administration, this period must be extended beyond the time during which adverse events are expected to occur. The duration of this interval must be discussed with the PI of the study.
- d. Immunotherapy: At least 6 weeks since the completion of any type of immunotherapy (e.g. tumor vaccines).

- e. Monoclonal antibodies: At least 3 half-lives must have elapsed since prior therapy that included a monoclonal antibody.

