If emesis occurs within 20 minutes of taking a dose of irinotecan, then the dose may be repeated once. If emesis occurs after 20 minutes, the dose should not be repeated. Instructions for administration of oral irinotecan are included in Appendix D and a copy of Appendix B, outlining potential drug interactions with irinotecan, should be given to the patient.

- 8.2.2 Adjustment of Dosing: This is defined in section 6.1 and 6.2 of the protocol
- 8.2.3 Source and pharmacology: Irinotecan is a semisynthetic water-soluble analog of camptothecin (a plant alkaloid isolated from Camptotheca acuminata). Irinotecan is a prodrug that requires conversion, by the carboxylesterase enzyme to the topoisomerase-I inhibitor, SN-38 in order to exert anti-tumor activity. SN-38 is approximately 1000 times more potent than irinotecan. Camptothecins interact specifically with the enzyme topoisomerase I which relieves torsional strain in DNA by inducing reversible single-strand breaks. Irinotecan and its active metabolite SN-38 bind to the topoisomerase I-DNA complex and prevent religation of these single-strand breaks. Current research suggests that the cytotoxicity of irinotecan is due to double-strand DNA damage produced during DNA synthesis when replication enzymes interact with the ternary complex formed by topoisomerase I, DNA, and either irinotecan or SN-38. Renal excretion is a minor route of elimination of irinotecan. The majority of the drug is metabolized in the liver. SN- 38 is conjugated to glucuronic acid and this metabolite has no anti-tumor activity. The extent of conversion of SN-38 to its glucuronide has been inversely correlated with the risk of severe diarrhea, because the other major route of SN-38 excretion is biliary excretion by canalicular multispecific organic anion transporter (cMOAT) which presumably leads to mucosal injury. In addition, APC and NPC are oxidative metabolites of irinotecan dependent on the CYP3A4 isoenzyme. After intravenous infusion of irinotecan in humans, irinotecan plasma concentrations decline in a multiexponential manner, with a mean terminal elimination half-life of about 6 to 12 hours. The mean terminal elimination half-life of the active metabolite SN-38 is about 10 to 20 hours. Irinotecan is 30% to 68% bound to albumin and SN-38 is approximately 95% bound to albumin.

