9. BIOMARKER, CORRELATIVE, AND SPECIAL STUDIES

9.1 Laboratory Correlative Studies

The plasma concentrations of eribulin as well as irinotecan, SN-38 and SN-38 glucuronide will be measured to assess drug disposition and pharmacokinetic parameters in each patient.

- 9.1.1 Pharmacokinetics
- 9.1.1.1 Collection of Specimen(s). Blood plasma samples for pharmacokinetics will be collected during cycle 1 on day 1 at pre-dose and at 15 minutes, 1 hour, 1.5 hours, 2 hours, 4 hours, and 5 hours after the start of the eribulin infusion and a pre-dose sample on day 8. These samples will be required for all patients. An optional sample between 24-96 hours may also be collected after the start of the eribulin infusion, from patients that are available for blood draw. Whole blood samples will be collected from the central line or a peripheral IV provided a flush of at least 10 ml of normal saline has been administered. At each time point, 7 ml of venous blood will be withdrawn into sodium heparinized collection tube. Please refer to Pharmacokinetic Study Form in Appendix G
- 9.1.1.2 Handling of Specimens(s). After collection, blood and anti-coagulant will be mixed by inverting the tube 8–10 times. Blood samples will be placed on ice immediately and centrifuged within 5 min at 7200 g at 4°C for 2 min. Plasma will be transferred into amber plastic tubes and stored on dry ice prior to transferring at -80°C until analysis. Plasma concentrations of free-base eribulin will be quantified using a validated liquid chromatography tandem mass spectrometry (LC/MS/MS) method as previously described [62]. Irinotecan, SN-38 and SN-38 glucuronide concentrations will be quantified using a validated HPLC method with fluorescence detection as previously described [63, 64].
- 9.1.1.3 Shipping of Specimen(s). Samples will be collected by study personnel in [name] lab for storage, processing and analysis. Please see Appendix G for additional information.

9.1.1.4 Site(s) Performing Correlative Study. University of Kentucky and Children's Hospital Colorado

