13.4 Analysis of Primary and Secondary Endpoints

All patients who received study drug will be included in the safety analysis of this combination regimen. Dose-limiting toxicity rate, adverse event data and corresponding toxicity grades during the days of treatment will be summarized in each dose level and in the overall patient population. Incidence tables will be generated to summarize incidence of patients reporting at least one episode of each specific adverse event, incidence of adverse events causing withdrawal and incidence of serious adverse events. The total number of episodes for each event reported (Frequency Table), and the severity and attribution to study therapy of each episode reported (Severity Table and Attribution Table) will also be displayed.

Listings of adverse events by patients will include the time to onset, the duration of each event, the severity of each event, and the relationship of the event to study therapy, whether it was a serious event, and whether it caused withdrawal. Safety data will be summarized for the overall patient group and by dose levels. Toxicities will be graded according to Common Toxicity Criteria (CTCAE) v4.02.

Estimates of antitumor effect based on RECIST 1.1 criteria will be estimated. Furthermore,

Protocol # 15-0659 Version Date: March 22, 2017

specific PD parameters will be assessed including SN-38 and SN-38 glucuronide. Descriptive statistics will be employed to summarize quantitative levels of PD parameters at each time point of follow-up while changes in PD from baseline will be calculated and compared using paired statistical tests. Pharmacokinetic modeling (two-compartment or non-compartmental models) will be employed to estimate several PK parameters (area under the concentration versus time curve, AUC, half-life, clearance, Cmax, etc). These analyses will be considered exploratory in this Phase I trial.

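### Section 13.4 treats SN-38 and SN-38 glucuronide as PD and tests them against an effectively empty baseline, so the p-values say nothing about the level of exposure

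*Combined protocol and SAP*

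**What the plan says.** Section 13.4 states that "specific PD parameters will be assessed including SN-38 and SN-38 glucuronide". It plans descriptive summaries of these levels at each follow-up time, and then that "changes in PD from baseline will be calculated and compared using paired statistical tests". It does not name the test, define baseline, or name any other PD marker. It goes on to plan PK modelling (AUC, half-life, clearance, Cmax) without saying for which analytes, and closes: "These analyses will be considered exploratory in this Phase I trial".

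Section 9.1 classes the same analytes differently: "The plasma concentrations of eribulin as well as irinotecan, SN-38 and SN-38 glucuronide will be measured to assess drug disposition and pharmacokinetic parameters". Section 2.3 gives the biology: "Irinotecan is converted into its active metabolite SN-38 in the liver by carboxylesterase enzymes". SN-38 is then conjugated to the glucuronide.

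Sampling (Sections 5.2 and 9.1.1.1) is in cycle 1 only: day 1 pre-dose, then 0.25, 1, 1.5, 2, 4 and 5 h counted from eribulin, a day 8 pre-dose sample, and one optional sample between 24 and 96 h. On day 1 irinotecan follows eribulin by a minimum of 15 minutes, with no maximum.

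Section 2.5 gives the study of exposure-toxicity relationships as the purpose of the PK sampling. The listed PK objective, 1.2.2, concerns eribulin only.

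**The concern.** SN-38 and its glucuronide are a drug metabolite and its conjugate. They measure how much drug reached the plasma, not what it did there. A change-from-baseline test suits an effect marker that has a meaningful value before treatment. Applied to a drug concentration with an empty pre-dose sample, it asks whether SN-38 appears after irinotecan is swallowed, which nobody doubts.

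The risk is a set of small p-values in the report that look like findings but do not say whether exposure was high or low. Meanwhile the question that Section 2.5 gives as the reason for drawing the samples, whether exposure relates to toxicity, has no analysis in Section 13.4. Averaging concentrations at nominal times counted from the other drug adds a separate blur.

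**Working it through.** The plan states no alpha, power or n for these tests, so there is no figure of its own to reproduce.

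**1. Which sample is the baseline?** Irinotecan comes no sooner than 15 minutes after eribulin, so only the cycle 1 day 1 pre-dose sample is certain to precede it.

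**2. How much SN-38 can that sample hold?** Section 3.1.5 says "Prior treatment with irinotecan or eribulin is allowed", but of myelosuppressive chemotherapy it says "Must not have received within three weeks of start date of this protocol chemotherapy". Section 8.2.3 states: "The mean terminal elimination half-life of the active metabolite SN-38 is about 10 to 20 hours". That figure is given in the context of intravenous dosing. The residual fraction is 2^(-t/half-life):
- 3 weeks = 504 h, half-life 20 h: 2^(-25.2) = 2.6e-8.
- 504 h, half-life 10 h: 2^(-50.4) = 6.7e-16.
- Only 7 days = 168 h, half-life 20 h: 2^(-8.4) = 0.0030, or 0.3%.
- 504 h with a half-life of 100 h, five times the stated upper figure: 2^(-5.04) = 0.030, or 3%.

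The baseline is effectively zero. The documents give no half-life for the glucuronide; the same conclusion is assumed for it because it is formed from SN-38.

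**3. What does the p-value depend on?** With a zero baseline, the change is the post-dose concentration.
- Sign or signed-rank test, all changes positive: two-sided p = 2 x 0.5^n. This gives 0.031 at n = 6, 3.1e-5 at n = 16 and 4.8e-7 at n = 22. Only n matters.
- Paired t: t = mean/(SD/sqrt(n)) = sqrt(n)/CV. Multiplying every concentration by one constant changes mean and SD alike, so t and p do not move.

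| n | CV (assumed) | t | p |
|---|---|---|---|
| 6 | 50% | 4.90 | 0.0045 |
| 6 | 100% | 2.45 | 0.058 |
| 16 | 50% | 8.00 | 8.6e-7 |
| 16 | 100% | 4.00 | 0.0012 |
| 22 | 50% | 9.38 | 5.9e-9 |
| 22 | 100% | 4.69 | 1.3e-4 |

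Here 6 and 22 are the accrual limits in Section 13.2, and 16 is 6 patients plus the 10 expansion patients at the RP2D. The CVs are assumptions; the documents give none.

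**4. Samples where step 3 does not apply as it stands.**
- 15 minutes: irinotecan has only just been given, or not yet, so the test may compare zero with zero.
- Day 8 pre-dose: about 72 h after the day 5 irinotecan dose. The fraction left is 2^(-72/20) = 8% to 2^(-72/10) = 0.7%, so the result may turn on whether the analyte is still detectable.

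**5. Are nominal times comparable?** If irinotecan is given 15 min, 1 h or 2 h after eribulin, all of which the protocol allows, the 2 h sample falls 1.75, 1 or 0 h after irinotecan.

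**6. How much of the curve does day 1 cover?** The last required day 1 sample is at most about 4.75 to 4.83 h after irinotecan, depending on whether the 5 h is counted from the start or the end of the infusion. That is 4.75/20 = 0.24 to 4.83/10 = 0.48 of one SN-38 half-life. The terminal phase is not covered, so a day 1 AUC is partial.

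**7. Could exposure-toxicity be tested instead?** The smallest correlation detectable with 80% power at two-sided 0.05 (assumed settings, Fisher z) is tanh(2.80/sqrt(n-3)): 0.92 at n = 6, 0.65 at n = 16, 0.57 at n = 22. Description is realistic; testing is not.

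**The case against.** A reader might infer that the p-value cannot depend on exposure in any way. The documents do not support that. Section 13.4 names no test, and the statement is exact only for a rank test in which every change is positive. A paired t-test responds to between-patient CV, which is a feature of the exposure distribution. At 15 minutes and possibly on day 8, detectability matters too, and on day 8 that can depend on clearance. What stands is narrower: the p-value is silent on the level of exposure, and the exceptions do not make it more useful.

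A reader might also infer that exposure will go unreported. It will not. Section 13.4 plans summaries of concentrations and estimates of AUC and Cmax, and Section 9.1 read with it brings irinotecan and both metabolites into the PK work. Appendix G records irinotecan administration and sample collection times, so the modelling can use actual times.

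It is also fair to say that the PD list is open-ended, that testing at every time point is not stated, that the half-life comes from intravenous dosing, and that the exposure-toxicity aim appears in background text and not in Section 1.2. These points limit the severity. They do not give the paired test a useful question, and the exploratory label does not supply one either.

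**Conclusion.** The point holds in limited form. Sections 9.1 and 13.4 disagree on whether the two metabolites are PK or PD, and the PD label leads to paired tests that show only that irinotecan was taken, absorbed and metabolised. Summaries by time from eribulin mix samples up to 1.75 h apart in time since irinotecan in the cases shown, and more if irinotecan is given later still. The aim in Section 2.5 has no stated analysis.

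Severity is low. The analyses are exploratory, the exposure-toxicity aim is not a listed objective, and no dose decision uses these results, so the RP2D is unaffected.

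The conclusion assumes that baseline means the day 1 pre-dose sample, that prior irinotecan falls under the three-week rule (a 7-day gap would still leave only 0.3%), and that the half-life given for intravenous dosing is a fair guide. The p-value ranges also rest on the assumed CVs. Differences in wording about where the optional sample may be drawn, and about whether sampling times run from the start or the end of the 2 to 5 minute eribulin infusion, are clerical and carry no weight here.

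**What to change.** In Section 13.4:
- List SN-38 and SN-38 glucuronide with irinotecan in the PK analysis, and delete the paired tests.
- State that the Cmax and AUC already planned cover these analytes, and add metabolite ratios. Label AUC over the sampled window as partial where the terminal phase is not covered.
- Base these on actual time since irinotecan, from the administration and collection times on the Appendix G form, not on nominal time from eribulin.
- Add a descriptive, exploratory display of individual exposure values against first-cycle DLT and worst toxicity grade, as Section 2.5 intends, with no p-values.

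The cost is a wording change and a small amount of extra descriptive analysis. No new samples, visits or data fields are needed. What is given up is a set of p-values that did not describe the level of exposure.

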13.5 Data Management

The study statistician and staff from the Biostatistics Shared Resource Facility (BSRF) of the Markey Cancer Center worked closely with the study investigators and the Clinical Research and Data Management (CRDM SRF) at Markey in the development of eCRFs for the study. Specifically, the statisticians attended several meetings including the Protocol Initiation Meeting (PIM) to address all statistical considerations for this protocol including incorporation of dose-escalation plans for this Phase I trial, appropriate and accurate collection of primary and secondary study endpoints and inclusion of valid values and range checks for data fields. Red Cap, managed by staff at CHCO, will be the primary database repository of clinical data from all patients enrolled into this trial. Data will be accessed by the study statistician on a regularly-scheduled basis to perform statistical programming for conduct of data quality control, data management, generation of interim reports and statistical analysis. The BSRF has developed an automated mechanism for generating a trigger for assessment of dose limiting toxicities based on the dose escalation rules in sections section 5.0 above. In collaboration with the study team, procedures will be developed for timelines for data quality control, resolution of data queries, interim reporting and final data analysis.

APPENDIX A	PERFORMANCE	STATUS CRITERIA

ECO)G Performance Status Scale	Karnofsky Performance Scale		
Grade	Descriptions	Percent	Description	
0	Normal activity. Fully active, able	100	Normal, no complaints, no evidence of disease.	
0	performance without restriction.	90	Able to carry on normal activity; minor signs or symptoms of disease.	
1	Symptoms, but ambulatory. Restricted in physically strenuous activity, but ambulatory and able	80	Normal activity with effort; some signs or symptoms of disease.	
	to carry out work of a light or sedentary nature (e.g. , light housework, office work).	70	Cares for self, unable to carry on normal activity or to do active work.	
2	In bed <50% of the time. Ambulatory and capable of all self-care, but unable to carry out	60	Requires occasional assistance, but is able to care for most of his/her needs.	
	any work activities. Up and about more than 50% of waking hours.	50	Requires considerable assistance and frequent medical care.	
2	In bed >50% of the time. Capable of only limited self-care, confined	40	Disabled, requires special care and assistance.	
3	to bed or chair more than 50% of waking hours.	30	Severely disabled, hospitalization indicated. Death not imminent.	
	100% bedridden. Completely disabled. Cannot carry on any	20	Very sick, hospitalization indicated. Death not imminent.	
self-care. Totally confined to or chair.		10	Moribund, fatal processes progressing rapidly.	
5	Dead.	0	Dead.	

APPENDIX B INFORMATION ON POSSIBLE DRUG INTERACTIONS

Information on Possible Interactions with Other Agents for Patients and Their Caregivers and Non-Study Healthcare Team

Irinotecan interacts with many drugs that are processed by your liver. Because of this, it is very important to tell your study doctors about all of your medicine before you start this study. It is also very important to tell them if you stop taking any regular medicine, or if you start taking a new medicine while you take part in this study. When you talk about your medicine with your study doctor, include medicine you buy without a prescription at the drug store (over-the-counter remedy), or herbal supplements such as St. John's wort.

Many health care prescribers can write prescriptions. You must also tell your other prescribers (doctors, physicians' assistants or nurse practitioners) that you are taking part in a clinical trial. **Bring this paper with you and keep the attached information card in your wallet**. These are the things that you and they need to know:

Irinotecan interacts with (a) certain specific enzyme(s) in your liver.

- The enzyme(s) in question is *CYP isoenzyme 3A4*. Irinotecan is broken down by this enzyme in order to be cleared from your system.
- **Irinotecan** must be used very carefully with other medicines that need these liver enzymes to be effective or to be cleared from your system.
- Other medicines may also affect the activity of the enzyme.
 - Substances that increase the enzyme's activity ("inducers") could reduce the effectiveness of the drug, while substances that decrease the enzyme's activity ("inhibitors") could result in high levels of the active drug, increasing the chance of harmful side effects.
 - You should notify your study doctor if you are prescribed: **phenytoin**, **phenobarbital**, **carbamazepine** or **ketoconazole** since these drugs are known to affect the levels of irinotecan in your body.
- You and healthcare providers who prescribe drugs for you must be careful about adding or removing any drug in this category.
- Before you start the study, your study doctor will work with your regular prescriber to switch any medicines that are considered "strong inducers/inhibitors or substrates of CYP 3A4."
- Your prescribers should look at this web site http://medicine.iupui.edu/clinpharm/ddis/table.aspx or consult a medical reference to see if any medicine they want to prescribe is on a list of drugs to avoid.
- Please be very careful! Over-the-counter drugs have a brand name on the label—it's usually big and catches your eye. They also have a generic name—it's usually small and located above or below the brand name, and printed in the ingredient list. Find the generic name and determine, with the pharmacist's help, whether there could be an adverse interaction.
- Be careful:
 - If you take acetaminophen regularly: You should not take more than 4 grams a day if you are an adult. Read labels carefully! Acetaminophen is an ingredient in

many medicines for pain, flu, and cold.

- If you drink grapefruit juice or eat grapefruit: Avoid these until the study is over.
- If you take herbal medicine regularly: You should not take St. John's wort while you are taking **Irinotecan**.

Other medicines can be a problem with your study drugs.

- You should check with your doctor or pharmacist whenever you need to use an over-the-counter medicine or herbal supplement.
- Your regular prescriber should check a medical reference or call your study doctor before prescribing any new medicine for you. Your study doctor's name is

and he or she can be contacted at

